1.3.1 Parkinson's Disease Psychosis Program

The scope of the development program for pimavanserin is the largest ever conducted in PDP. At the time of approval, 616 mostly older, late-stage PDP subjects had been evaluated in 16 countries over a span of >10 years. Clinically meaningful efficacy was established in Study ACP-103-020, a 6-week, placebo-controlled Phase 3 study (Cummings et al. 2014). This efficacy was supported by data from additional short-term Phase 2b/3 studies. In ACP-103-020, pimavanserin 34 mg consistently demonstrated statistically significant efficacy across multiple and independent endpoints, subject subgroups, and sensitivity analyses. Improvements in sleep and daytime wakefulness were also observed. These clinical

benefits were achieved without worsening of Parkinson's disease motor symptoms and without a number of other safety concerns associated with atypical antipsychotics.

Pimavanserin is considered to be generally safe and well tolerated. Across all clinical studies of pimavanserin, the most frequently reported treatment-emergent adverse events (TEAEs) were in the central nervous system (CNS), gastrointestinal, and psychiatric systems. Most events were mild to moderate in intensity. The most common CNS TEAEs included dizziness (including postural), headache, and somnolence (drowsiness). Common gastrointestinal disturbances included dyspepsia, nausea, constipation, and vomiting. Severe nausea and vomiting were dose limiting in a few cases. Reported psychiatric conditions included agitation, insomnia, and confusional state.

Clinical and nonclinical safety pharmacology studies of pimavanserin suggest a potential risk for QT prolongation. The magnitude of effect in humans has been assessed in a thorough QT study with doses of pimavanserin ranging from 17 to 68 mg. In the Phase 3 PDP program, an average prolongation of approximately 5 to 8 ms was observed with pimavanserin 34 mg.

The US package insert for pimavanserin has a boxed warning that elderly patients with dementia-related psychosis treated with antipsychotic drugs are at an increased risk of death. Pimavanserin is not approved in the treatment of patients with dementia-related psychosis unrelated to the hallucinations and delusions associated with Parkinson's disease psychosis.

Additional information is provided in the pimavanserin Investigator's brochure and in the NUPLAZID[®] (pimavanserin) US package insert.

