7 ADVERSE EVENTS

7.1 Specification of Safety Parameters

7.1.1 Definition of Adverse Event

An AE is defined as “any untoward medical occurrence associated with the use of a drug in humans, whether or not considered drug related” ([US FDA 2012b](#)).

An AE can therefore be any unfavorable and unintended sign (e.g., an abnormal laboratory finding), symptom, or disease temporally associated with the use of a drug, without any judgment about causality or seriousness. An AE can arise from any use of the drug (e.g., off-label use, use in combination with another drug) and from any route of administration, formulation, or dose, including an overdose.

A suspected adverse reaction is any AE for which there is a reasonable possibility that the drug caused the AE.

AEs do not include the following:

- Stable or intermittent chronic conditions (such as myopia requiring eyeglasses) that are present prior to Baseline and do not worsen during the study
- Medical or surgical procedures (e.g., surgery, endoscopy, tooth extraction, transfusion). The condition that leads to the procedure is an AE if not present at the open-label Baseline.
- Overdose of either study drug (see [Section 7.4.4](#)) or concomitant medication without any signs or symptoms unless the subject is hospitalized for observation
- Hospitalization for elective surgery planned prior to study (situation where an untoward medical occurrence has not occurred)
- Pregnancy will not be considered an AE, but if it occurs, it will be reported on a pregnancy form

Adverse events will be recorded from the time informed consent is obtained through 30 days after the last dose of study drug.

All AEs must be either resolved or stable at end of study. If ongoing at the end of the study the subject should be referred for appropriate treatment.

Serious AEs occurring after the safety follow-up period should be reported if in the judgment of the Investigator, there is “a reasonable possibility” that the event may have been caused by the study drug.

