The Data Safety Monitoring Board (DSMB) will monitor, review, and evaluate the unblinded safety data on a periodic basis. In addition, the DSMB will review the results of the pre-planned unblinded interim analysis conducted by the Independent Statistical Group.

Pharmacokinetic samples will be collected at Weeks 13, 22, and 38/EOT. Pharmacokinetic samples will also be collected, if possible, at any ET visit or the visit immediately following any SAE or following an AE leading to discontinuation.

Safety Follow-up Period (Approximately 4 Weeks)

Approximately 4 weeks after the last dose of study drug, subjects will have a safety follow-up telephone call visit.

The Sponsor will provide investigative sites with 3 months of after-study assistance to transition subjects to standard of care therapy after their participation in the study.

Table 1 Schedule of Assessments for Screening and Open-label Period

	Screening	Open-label Period				
Visit week	-5 to 0	0	2	4	8	12 ^a
Allowable visit window (# days)			±3	±3	±3	+7
Visit Number	1	2	3	4	5	6
Informed consent	X					
Inclusion/exclusion criteria assessment	X	X				
Medical history and demographics	X					
Mini-Mental State Examination	X	X	X	X	X	X
MRI or CT ^b	X					
Psychosocial therapy training	X					
Physical and neurological examinations	X	X				X
Vital signs and weight	X	X	X	X	X	X
Height	X					
12-lead electrocardiogram ^c	X	X	X			X
Clinical laboratory tests	X	X				X
Pregnancy test ^d	X	X				X
SAPS-H+D	X	X	X	X	X	X
Clinical Global Impression-Improvement ^e			X	X	X	X
Clinical Global Impression-Severity	X	X	X	X	X	X
Zarit Burden Interview ^f		X				X
Karolinska Sleepiness Scale		X				X
EQ-5D-5L		X				X
Assessment for response criteria					X	X
Assessment for concomitant medications	X	X	X	X	X	X
Global Clinician Assessment of Suicidality	X	X	X	X	X	X
Extrapyramidal Symptom Rating Scale A		X				X
Assessment for adverse events	X	X	X	X	X	X
Pharmacokinetic sample collection ^g		X			X	X
Pharmacogenomic sample collection ^h		X				
Drug dispensation		X	X	X	X	X ⁱ
Drug return and accountability			X	X	X	X
Randomization						X

Footnotes for Table 1 on next page

Abbreviations: CT=computed tomography; MRI=magnetic resonance imaging;
SAPS-H+D=Scale for the Assessment of Positive Symptoms, Hallucinations and Delusions
subscales

Note: All efforts should be made to complete visits in a single day. In the event of a split visit, the CGI-S/CGI-I and the SAPS H+D must be completed on the same day (pertinent for all visits).

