3.4 Determination of Sample Size

This study will enroll approximately 356 subjects in order to randomize approximately 178 subjects with dementia-related psychosis who meet response criteria at Weeks 8 and 12 of the open-label period.

The sample size calculation was based on the following assumptions: a placebo relapse event rate of 60% over 26 weeks; a pimavanserin relapse event rate of 35% over 26 weeks (hazard ratio = 0.47); a dropout rate of 25% over 26 weeks; an overall two-sided alpha level of 0.05; use of a one-sided (0.025) O’Brien-Fleming stopping boundary to adjust for a single interim

analysis that will be performed when one half of the total planned number of post-randomization relapse events have occurred; and a power of 90%. The total number of post-randomization relapse events required at the final analysis is 75 and the calculated sample size is 89 in each of the two treatment groups (giving a total estimate of 178 subjects). Study enrollment will be closed when approximately 178 subjects have been randomized in the double-blind period or when 75 adjudicated post-randomization relapse events have occurred. In the event that the randomization rate is lower than anticipated and/or the relapse event rate is lower than anticipated, the number enrolled and randomized may be increased up to a maximum of 400 randomized subjects in order to observe 75 post-randomization relapse events. If fewer than 75 post-randomization relapse events have been observed after 400 randomized subjects have completed the study or terminated early, the study will end. An interim efficacy analysis will be performed, and the study may be terminated early if the interim analysis results meet prespecified stopping criteria.(see [Section 16](#))

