14.1 Adverse Events

All Adverse events (AEs) will be coded using MedDRA version 20.0 or newer.

An AE (classified by preferred term) will be considered a treatment emergent AE (TEAE) if the onset date was on or after the date of first dose of open-label pimavanserin and up to 30 days past the last dose of study drug. AEs reported on Day 1 based on open-label Baseline (pre-dose) findings (e.g. clinically significantly abnormal vital signs, laboratory test results, or electrocardiogram parameters) will not be considered as TEAEs.

Each TEAE will be assigned to either the open-label or double-blind period based on the onset date. For randomized subjects, if the onset date was on or after the date of first dose of double-blind study drug, the TEAE will be assigned to the double-blind period. All other TEAE will be assigned to the open label period.

The event counts and the number and percentage of subjects reporting TEAEs will be tabulated by SOC and preferred term; and, by SOC, preferred term, and maximum severity. If more than 1 AE occurs with the same preferred term for the same subject, the subject will be counted only once for that preferred term using the most severe occurrence for the

summarization by severity. In addition, the event counts and the number and percentage of subjects with TEAEs classified by the Investigators as related to the study drug, with most frequently reported TEAEs (preferred terms reported by $\geq 5\%$ of subjects overall for the open-label period and $\geq 5\%$ of subjects in either treatment group for the double-blind treatment period), with treatment emergent serious AEs, with fatal AEs (i.e. events that cause death), and with TEAEs leading to discontinuation of study drug will be summarized by SOC and preferred term. The display in these tables will be sorted alphabetically by SOC and then by descending subject frequency for the preferred terms using combined counts from both groups within each SOC. The event counts and the number and percentage of subjects with any TEAEs will also be tabulated by preferred term without SOCs. This table will be sorted by descending subject frequency using combined counts from all subjects.

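### Deaths are systematically collected only to about 30 days after the last dose, and fatal AEs are reported as crude percentages, although relapse is assumed to end dosing sooner on placebo

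*SAP*

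**What the plan says.** Under Protocol 3.4 and SAP 3.1, a subject who meets any relapse criterion comes off study drug and moves to safety follow-up. That follow-up is one telephone contact: "Approximately 4 weeks after the last dose of study drug, subjects will have a safety follow-up telephone call visit". Protocol 6.3.8 limits the call to adverse events and concomitant medication.

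Protocol 7.1.1 records AEs through 30 days after the last dose, and SAP 14.1 counts an event as treatment-emergent "up to 30 days past the last dose of study drug". SAP 14.1 summarizes fatal AEs by event count and by number and percentage of subjects.

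Some capture goes further. Protocol 7.1.1 adds: "Serious AEs occurring after the safety follow-up period should be reported if in the judgment of the Investigator", drug causation is a reasonable possibility. Protocol 4.4 and 7.4.2 follow SAEs that are already open until they resolve or become chronic or stable.

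We found no vital-status check for all randomized subjects at nominal Week 38, no time-to-death analysis and no exposure-adjusted death rate.

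The safety objective (Protocol 2.4) is a comparison with placebo. Protocol 1.3.1 cites the boxed warning that "elderly patients with dementia-related psychosis treated with antipsychotic drugs are at an increased risk of death".

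**The concern.** Observation for death ends at a time set by relapse or withdrawal. If the drug prevents relapse as assumed, placebo subjects leave earlier and are watched for death for less time. A crude percentage divides by everyone dosed and ignores that difference, so equal mortality would look like excess mortality on pimavanserin. Deaths after the window that nobody attributes to study drug need not be reported at all, so the 26-week comparison as randomized loses events. At stake is how reliably the trial describes the one class risk that the protocol itself names.

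**Working it through.** **Inputs from SAP 3.4 (also Protocol 9.3).** "a placebo relapse event rate of 60% over 26 weeks", 35% on pimavanserin, and "a dropout rate of 25% over 26 weeks", with 89 per arm. Assumptions: exponential times, and dropout equal in both arms. Weekly hazards:

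- placebo relapse: −ln(0.40)/26 = 0.03524
- pimavanserin relapse: −ln(0.65)/26 = 0.01657
- dropout: −ln(0.75)/26 = 0.01106

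**Reproducing the plan first.** HR = ln(0.65)/ln(0.40) = 0.470. Schoenfeld's formula gives 73.8 events, or 74.3 with one O'Brien-Fleming look, hence the stated 75. With competing dropout the 26-week relapse probabilities are 0.533 and 0.307, mean 0.420, and 75/0.420 gives about 178.6 against the stated 178. The inputs are therefore read as the plan uses them.

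**Time unobserved for death.** Let L be the exit hazard (relapse plus dropout): 0.0463 on placebo and 0.0276 on pimavanserin. Let g = 30/7 = 4.29 weeks, so 26 − g = 21.71.

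- Share whose window closes before Week 26 = 1 − exp(−21.71 L): 63% and 45%. Then 89 × 0.634 + 89 × 0.451 = 56 + 40, about 97 of 178.
- Share of 26-week person-time unobserved = [21.71 − (1 − exp(−21.71 L))/L]/26.
  - Placebo: (21.71 − 13.69)/26 = 30.8%, mean window 17.98 weeks.
  - Pimavanserin: (21.71 − 16.33)/26 = 20.7%, mean window 20.61 weeks.
  - Mean of the two arms: 25.8%.

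With a death hazard that is constant and unchanged by stopping drug, these are also, to a close approximation, the shares of 26-week deaths outside collection.

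**Sensitivity** (lag of exactly 4 weeks; 30 days gives slightly lower figures):

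| Case | Placebo | Pimavanserin | Mean |
|---|---|---|---|
| Plan rates | 31.5% | 21.2% | 26.4% |
| Relapse only, no dropout | 25.7% | 13.7% | 19.7% |
| Relapse 40% / 25% | 23.1% | 17.6% | 20.4% |
| Relapse 30% / 15% | 19.4% | 14.3% | 16.8% |
| Death hazard falling (Weibull shape 0.7) | 25.2% | 16.8% | 21.0% |
| Death hazard rising (Weibull shape 1.5) | 39.0% | 26.4% | 32.7% |
| Relapse 60% in both arms | 31.5% | 31.5% | 31.5% |

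**Effect on the planned table.** The documents give no mortality assumption. As an illustration, take the Phase 2 figure in Protocol 1.3.2 (4 deaths among 90 randomized to pimavanserin) and treat it as a 12-week risk: h = −ln(1 − 4/90)/12 = 0.0038 per week, equal in both arms.

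- Deaths by Week 26: 89 × (1 − exp(−26h)) = 8.35 per arm.
- Captured per arm = 89 × {1 − exp(−hg) + exp(−hg) · [h/(h + L)] · [1 − exp(−21.71(h + L))]}: 5.82 on placebo and 6.65 on pimavanserin.
- Crude percentages: 5.82/89 = 6.5% and 6.65/89 = 7.5%. The ratio 6.65/5.82 is 1.14.
- Missed overall: 1 − (5.82 + 6.65)/16.70 = 25%.
- At half that hazard, 4.28 deaths per arm with 2.97 and 3.40 captured. The ratio is again 1.14.

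**What a rate would do.** Person-weeks observed in this model are 1,537 and 1,757. Then 5.82/1,537 and 6.65/1,757 are both 0.0038 per week, so the arm difference disappears.

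**The case against.** The strongest reply is that an on-treatment plus 30 days window is coherent, and that all-cause 26-week mortality is not a listed endpoint. Everyone on placebo has already had 12 weeks of pimavanserin. Relapsers may move to other antipsychotics carrying the same class warning, more of them on placebo, so a full 26-week comparison could dilute a drug effect. This stands as a reason to show both analyses. It does not defend crude percentages over unequal windows.

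A reader might infer that deaths after 30 days are never collected. The documents do not support that: possibly drug-related SAEs and SAEs already open are captured later. That capture is selective, so the missed shares above are upper figures.

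A reader might also infer that exposure adjustment cannot help. Under independent exit it removes the arm imbalance, as shown above. What it cannot do is recover the uncollected deaths, or protect against a death risk that changes with relapse or stopping.

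The absolute numbers are small and the mortality source is a poor match: a single-center nursing-home study, mean age 85.9, against clinic-attending subjects who have responded for 12 weeks. At that rate the captured counts differ by only about 0.8 deaths. Full capture would narrow an approximate 95% CI for a rate ratio of 1 from 0.33–3.05 to 0.38–2.6, a modest gain. Death is also a listed discontinuation reason. If deaths form part of the 25% dropout, the missed share at the Phase 2 rate is 29.0% and 18.3%, mean 23.7%.

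**Conclusion.** The concern holds in a limited form. Systematic death capture stops about 30 days after the last dose, the planned fatal-AE display takes no account of follow-up time, and under the design assumptions the windows differ by arm. Up to about 31% (placebo) and 21% (pimavanserin) of nominal 26-week person-time is unobserved for death, or about 26% of 26-week deaths under a constant hazard. The main alternatives run from roughly 20% to 33%, and 30%/15% relapse gives 17%. With equal mortality, crude percentages would show about 14% more deaths on pimavanserin.

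Three limits apply. The quarter needs dropout as well as relapse; relapse alone gives about 20%. The imbalance follows from the assumed relapse difference and vanishes without it. The figures also assume that every subject could reach 26 weeks, so an earlier study discontinuation date would reduce the 97 early leavers. It would be tempting to conclude that the mortality comparison is beyond repair, but that would require death risk to depend on exit, and the documents give no information on that.

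**What to change.** 1. In SAP 14.1, add all-cause mortality from randomization by randomized arm, beside the on-treatment plus 30 days table: Kaplan-Meier, and deaths per person-time with 95% CI. Deaths and person-time must use the same window, so that selectively reported later deaths do not enter the numerator alone. This needs no new data and removes the unequal-follow-up artefact if death risk does not depend on exit.
2. To recover lost events and guard against exit-related risk, add one eCRF item (alive or dead, with date) at nominal Week 38 or the study discontinuation date, whichever comes first. Collect it by telephone or record check for randomized subjects who have not withdrawn consent to contact, and have the consent form cover it.

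The after-study support in SAP 3.1 should not be the collection route: "The Sponsor will provide investigative sites with 3 months of after-study assistance to transition subjects to standard of care therapy". It is support to sites, not data collection. Counted from 30 days after the last dose, it would end before Week 38 for anyone leaving before about week 8.7 of the double-blind period (26 − 4.3 − 13). That is 89 × 0.332 + 89 × 0.214, about half of the 97.

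Cost: a short amendment and some site effort for about 97 subjects, with no added visit or test. Capture will remain incomplete for subjects lost to follow-up. Later deaths may follow other antipsychotics, which is why both tables should be shown.

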3.2 Randomization

At Week 12 (Visit 6), subjects who meet response criteria will be randomized in a 1:1 ratio to either continue receiving pimavanserin at the current dose level or to receive matched placebo, using an interactive response technology system. Randomization will be stratified by:

- Most likely dementia subtype or most prominent cause of dementia (defined as designated dementia subtype):
 - Alzheimer’s disease or frontotemporal dementia (FTD) spectrum disorders
 - Vascular dementia
 - Parkinson’s disease dementia or dementia with Lewy bodies
- Region (North America, Western Europe, Eastern Europe, Asia Pacific, Latin America)

The assignments will be based on a pre-generated permuted-block randomization schedule. Blinding will be assured by restricting access of Investigators and Sponsor personnel and/or designee to the treatment codes, and providing identical tablets and packaging for the pimavanserin and placebo treatments.

3.3 Blinding

All subjects will receive open-label pimavanserin (34 mg or 20 mg) during the open-label period of the study.

Treatment assignment during the double-blind period will be double-blind such that neither the subjects, study partners/caregivers, Sponsor personnel who oversee the study, nor the Investigator and study personnel will know which treatment is assigned to each subject.

3.4 Determination of Sample Size

This study will enroll approximately 356 subjects in order to randomize approximately 178 subjects with dementia-related psychosis who meet response criteria at Weeks 8 and 12 of the open-label period.

The sample size calculation was based on the following assumptions: a placebo relapse event rate of 60% over 26 weeks; a pimavanserin relapse event rate of 35% over 26 weeks (hazard ratio = 0.47); a dropout rate of 25% over 26 weeks; an overall two-sided alpha level of 0.05; use of a one-sided (0.025) O’Brien-Fleming stopping boundary to adjust for a single interim

analysis that will be performed when one half of the total planned number of post-randomization relapse events have occurred; and a power of 90%. The total number of post-randomization relapse events required at the final analysis is 75 and the calculated sample size is 89 in each of the two treatment groups (giving a total estimate of 178 subjects). Study enrollment will be closed when approximately 178 subjects have been randomized in the double-blind period or when 75 adjudicated post-randomization relapse events have occurred. In the event that the randomization rate is lower than anticipated and/or the relapse event rate is lower than anticipated, the number enrolled and randomized may be increased up to a maximum of 400 randomized subjects in order to observe 75 post-randomization relapse events. If fewer than 75 post-randomization relapse events have been observed after 400 randomized subjects have completed the study or terminated early, the study will end. An interim efficacy analysis will be performed, and the study may be terminated early if the interim analysis results meet prespecified stopping criteria.(see [Section 16](#))

4 ANALYSIS SETS

4.1 Intent-to-treat (ITT) Analysis Set

The ITT Analysis Set will include all randomized subjects. Subjects will be analyzed based on their randomized treatment. The ITT Analysis Set will be used for analyses of the double-blind efficacy data.

4.2 Open-label Safety Analysis Set

The Open-label Safety Analysis set will include all subjects who received at least one dose of open-label study drug (pimavanserin). The Open-label Safety Analysis Set will be used for analyses of the open-label data.

4.3 Double-blind Safety Analysis Set

The Double-blind Safety analysis set will include all subjects who received at least one dose of double-blind study drug (pimavanserin or placebo). Subjects will be analyzed based on the treatment that they actually received. The Double-blind Safety Analysis Set will be used for all analyses of the double-blind safety data.

